5.6 Description of Treatment and Definition of Exposure to trial medication

Not applicable as there will be no use of any trial medication. Subjects’ embryos will be observed using morphological assessments as standard of practice at the IVF laboratories and a part of the trial patients in an allocation ratio of 2:1 will be assigned to have EEVA Time Lapse system embryos observation and assessments added to their standard assessment. Culture conditions and elements will be the same for all embryos in the laboratory regardless of their allocation at randomization.

5.7 Criteria for Subject Withdrawal

Subjects will be informed that they have the right to withdraw from the trial at any time without prejudice to their medical care, and that they are not obligated to state their reasons. Any withdrawal must be fully documented in the source documents

Subject data will be included in the analyses up to the time that consent was withdrawn. The trial exit electronic case report form should be completed at the time a subject is exited from the trial.

The sponsor reserves the right to discontinue this trial at any time.

6 Trial Endpoints and Assessment Procedures

Embryos will be observed until they are transferred and then subjects' outcomes information will be collected for all subjects until implantation and pregnancy are verified (up to 8 weeks after embryo transfer). Additional follow up to determine final pregnancy outcome may be included if available.

Subjects will be followed up until loss to follow-up, occurrence of an exclusion criterion, or the end of the data collection period, whichever comes first.

6.1 Endpoints

Primary Endpoint: Implantation rate from embryo transfers performed on day 3 or day 5.

Secondary Endpoints: Utilization rate, Clinical pregnancy rate, Ongoing pregnancy rate, Multiple pregnancy rate, Spontaneous miscarriage rate.

Endpoints are defined as follows :

- Implantation rate (number of sacs with fetal heart beat/ total number of embryos transferred)
- Utilization rate (transferred + frozen/ fertilized eggs) X100.
- Clinical pregnancy rate (at approximately 5-8 weeks gestational age)
- Multiple pregnancy rate defined as a clinical pregnancy with ≥ 2 fetal sacs.
- Spontaneous miscarriage rate as a desired follow-up endpoint.

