blastocyst stage. The user has the ability to export image data, embryo reports, and movies. The images are acquired while embryos are developing inside standard incubators. In case of any Eeva malfunction the subsequent development of the embryos will not be affected in any way and the only missing piece will be the automatic recommendation by the computer.

The optimal goal of IVF/ICSI should be the delivery of a healthy singleton baby.³⁻⁵ The clinical dilemma, is how to reduce the number of embryos for transfer to prevent multiple births while at the same time maintaining or improving IVF/ICSI success rates.

Currently, embryos are being selected based on traditional morphology scores developed in the early 1980s, which are based on multiple observations of embryos under regular light microscopes.⁶⁻⁹ However, it is that traditional morphology grading, which only captures static images at a few time points, is of very limited predictive value. It was reported that only 51% of embryos transferred on Day 5 were pre-selected for transfer on Day 3.¹⁰ In a controlled Trial, embryologists were asked to choose 2 embryos with optimal potential for blastocyst development using traditional morphology grading criteria. Results showed that morphology criteria assessed on Day 3 did not accurately predict blastocyst formation. In 39% of cycles neither choice resulted in blastocyst formation, and in 38% of cycles 1 assessment resulted in a blastocyst transferred. Embryologists were able to pick the best 2 embryos in just 23% of cycles.¹¹

Recently, researchers from Stanford University reported results that correlated time-lapse image analysis with gene expression profiling of pre-implantation human embryo development.¹² It was discovered that success in development to the human blastocyst stage can be predicted accurately from dynamic, non-invasive imaging parameters that are observed prior to embryonic genome activation (on Day 3). These parameters can be reliably measured by way of automated image analysis, confirming that successful development follows a set of carefully orchestrated and predictable events. Moreover, image phenotypes reflected underlying molecular programs of the embryo and individual blastomeres. This was the first trial to report that dynamic morphology parameters of embryo development reflect underlying molecular program status and provide a promising platform for early assessment of embryo viability.¹²

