6.3.7 Gestational Age Week 5-8

The first ultrasound to verify clinical pregnancy will be recorded on the **Transfer and Treatment Outcome** eCRF including:

- Date of ultrasound
- Result of initial pregnancy ultrasound
 - Number of intrauterine gestational sacs
 - Number of fetal heartbeats

If the result of the ultrasound is negative, that is, if no fetal heartbeat is detected, then the subject will have completed the trial and be exited at that time (complete **Trial Exit** electronic case report form).

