6.3.9 Additional Ultrasound > 8 weeks (Optional)

Any additional vaginal ultrasounds performed after 8 weeks may be recorded on an **Additional Ultrasound** eCRF. The collection of this data is optional, however encouraged.

Data will include the following:

- Date of ultrasound
- Result of initial pregnancy ultrasound
 - Number of fetal sacs and number of fetal heartbeats

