5.2 Secondary endpoints

- (a) Utilization Rate (UR) (number of transferred and frozen embryos divided by number of normally fertilized oocytes x 100),
- (b) Clinical Pregnancy Rate (CP) (assessed by ultrasonography at weeks 5 to 8),
- (c) Ongoing Pregnancy Rate (OP) (assessed by ultrasonography at weeks 10 to 12),
- (d) Multiple Pregnancy Rate (MP) (assessed by ultrasonography at weeks 5 to 8) and
- (e) Spontaneous Miscarriage (SM).
- (e) Drugs protocol type (GnRH agonist/GnRH antagonist) and gonadotrophin dose for Controlled Ovarian Stimulation in relation with Eeva categories and implantation outcomes.

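### Multiple pregnancy is defined by sac count alone, so twins sharing one sac are scored as singletons although heartbeats are counted at the same scan

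*Protocol*

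**What the plan says.** Protocol 6.1 defines the endpoint: "Multiple pregnancy rate defined as a clinical pregnancy with ≥ 2 fetal sacs". It sets no heartbeat condition. In the same list the primary endpoint does carry one: "Implantation rate (number of sacs with fetal heart beat/ total number of embryos transferred".

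The other places that name the endpoint add only when it is assessed. Protocol 4.2 and 7.4.2 do so, and SAP 5.2 reads "Multiple Pregnancy Rate (MP) (assessed by ultrasonography at weeks 5 to 8". SAP 14.4 and 14.5 promise an estimate and 95% CI in the EMG, MG, EC and ENC groups, for the ITT and KID selections, without a derivation.

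The data for a fuller rule are collected. Protocol 6.3.7 lists "Number of intrauterine gestational sacs" and "Number of fetal heartbeats" as separate items of the same scan, and SAP 17 carries them as Nsac and Nhbt. SAP 19.2.6 plans sac and heartbeat counts by treatment group.

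**The concern.** The rule counts sacs, while the endpoint's name refers to the number of fetuses. The two differ when twins lie in one sac, and the rule cannot see such a pregnancy. They may also differ when a second sac has no heartbeat.

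The endpoint bears on a problem that the protocol itself raises. Its background section describes the clinical dilemma as "how to reduce the number of embryos for transfer to prevent multiple births" while keeping success rates up. Multiple pregnancy is the listed endpoint closest to that issue. With no derivation in the SAP, a programmer would apply the rule in 6.1, and the reported rate would omit pregnancies that the trial's own scan shows to be twins.

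**Working it through.** The documents state no figure for multiple pregnancy, so there is none to reproduce. The check applies the rule to each scan result and then sizes the gap under stated assumptions.

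**Step 1: classification.** I take a clinical pregnancy to be a scan with at least one heartbeat. Protocol 6.3.7 supports this by calling the scan negative when there is none: "if no fetal heartbeat is detected, then the subject will have completed the trial". *Fetal sac* is read literally here.

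| Sacs | Heartbeats | Rule in 6.1 (sacs ≥ 2) | Heartbeats ≥ 2 | Either ≥ 2 |
|---|---|---|---|---|
| 1 | 1 | single | single | single |
| 1 | 2 | **single** | multiple | multiple |
| 2 | 1 | multiple | **single** | multiple |
| 2 | 2 | multiple | multiple | multiple |

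The sac and heartbeat rules disagree in exactly two rows.

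**Step 2: does the disagreement depend on what *fetal sac* means?**
- One sac, two heartbeats: no. There is one sac on any reading, so the rule misses this twin pregnancy.
- Two sacs, one heartbeat: yes. Protocol 6.3.9 lists "Number of fetal sacs and number of fetal heartbeats" as two counts, which favours the literal reading, as does the contrast within 6.1. But Protocol 7.4.1 and 7.6.2 use total fetal sacs as the implantation numerator, where 4.1 and 6.1 require a heartbeat. If a fetal sac means a sac with a heartbeat, this pregnancy is not a multiple under the rule.

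**Step 3: size of the certain error.** Assume 400 clinical pregnancies in a group, and one-sac twins making up a share s = 0.5% to 2% of them. Both inputs are assumptions.

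Missed twins = 400 × s = 400 × 0.005 = 2, up to 400 × 0.02 = 8.

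Assume further that 12% have at least two sacs, that is 48 of 400. The rule in 6.1 reports 48/400 = 12.0%. Counting either sacs or heartbeats gives (48 + 2)/400 = 12.5% to (48 + 8)/400 = 14.0%.

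**Step 4: both directions, on the literal reading.** Assume also that a share v = 10% to 30% of two-sac pregnancies show one heartbeat.

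Heartbeat-based count = 48 × (1 − v) + 400 × s.
- Lowest: 48 × 0.70 + 2 = 35.6, or 8.9%.
- Highest: 48 × 0.90 + 8 = 51.2, or 12.8%.

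This range contains the sac-rule value of 12.0%, so the two errors can cancel in the total. For scale, the 95% half-width for 48/400 is 1.96 × √(0.12 × 0.88 / 400) = 3.2 percentage points.

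**Step 5: do the planned tables already show it?** Write b for the number with two sacs and one heartbeat, and c for the number with one sac and two heartbeats. Separate counts of sacs and heartbeats reveal only the difference c − b. With 48 two-sac pregnancies, b = 5 and c = 5, both tables show 48 women with two or more, while 48 + 5 = 53 meet one criterion or the other. The missed twins cannot be recovered from the two tables.

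**The case against.** The strongest reply is that little is lost. The endpoint is secondary, SAP 14.1 calls the study purely descriptive, and the SAP plans no test of this endpoint between arms. Heartbeat counts by arm are already in SAP 19.2.6, so a reader could find how many women in each arm had two or more. Counting sacs may also be deliberate: the scan may fall as early as week 5, when a second heartbeat may not yet be visible, and a rule based only on heartbeats could then score such twins as singletons.

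Most of this stands and limits the weight of the point. It is also the reason not to replace the sac count with a heartbeat-only rule; which of the two is better is a trade-off that the documents do not settle. It does not remove the one-sac case. The planned tables do not cross sacs with heartbeats, and neither of them carries the label of multiple pregnancy.

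A reader might go further and infer that the rule favours Eeva. After a single transfer a multiple arises only from splitting of the embryo, so the likely error there is a missed one-sac twin. After a transfer of several embryos, an empty second sac could add to the count. If Eeva moved women towards single transfer, the errors would differ by arm. The documents do not support that step. Protocol 6.3.4 leaves transfer to each site's standard practice, Protocol 8.1 has the investigator set the treatment strategy regardless of trial participation, and nothing predicts a different number of embryos transferred by arm. The background remark on multiple births describes IVF in general; the trial's stated aim is to predict implantation potential.

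**Conclusion.** The point holds in a limited form. On any reading of *fetal sac*, the rule in Protocol 6.1 scores twins in one sac as a singleton, and the SAP does not correct this although both counts are in the database. The treatment of two sacs with one heartbeat is unsettled, because the term is undefined and used inconsistently. That is a gap in terminology and not a demonstrated second error.

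The size is small: 2 to 8 missed twin pregnancies per 400 clinical pregnancies, resting wholly on the assumed 0.5-2%. The documents supply no rate against which to check it. No bias towards either arm is shown, and the numerator of the implantation rate is a separate matter. This is a minor correction to a descriptive secondary endpoint in an exploratory trial.

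**What to change.** - In Protocol 6.1 and SAP 5.2 and 14.4, define multiple pregnancy as a clinical pregnancy with at least two fetal sacs or at least two fetal heartbeats at the week 5-8 scan, derived from Nsac and Nhbt. The same derivation then carries into SAP 14.5.
- Define *fetal sac* once, stating whether a heartbeat is required, and use it consistently in both documents.
- Report the rate with at least two heartbeats as an additional row by arm, beside the rate with at least two sacs. This shows how far the result depends on the criterion, including any pregnancies with two sacs and one heartbeat.

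The cost is a line or two in each document and one extra table row, with no new data. The combined rate is slightly less directly comparable with purely sac-based rates; keeping the sac-based row answers that.

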6.2 Potential Confounding Factors

There are no expected major confounding factors that would contribute to determine the outcomes on either one of the arms related to the main variables, that is, use or not of Eeva technology for embryo assessment in addition to standard morphological assessment. Such standard scoring and grading conventions will be provided to sites to capture accordingly in the eCRFs.

6.3 Frequency of Assessments

6.3.1 Baseline Information and hCG Trigger Day

Enrolled subjects in the trial will undergo pre-IVF/ICSI preparations per the standard protocol currently in force for each site. Collection of trial-related information may take place only after the subject and partner, if applicable, has given voluntary, documented, informed consent and will include the following information, which will be recorded on the baseline electronic case report form including:

- Demographics
- Pregnancy history
- Prior ART
- Cycle Day 3 hormones (FSH, AMH, Estrogens, LH, etc)
- Cause of Infertility
- Protocol of Stimulation
- Time of hCG trigger to oocyte retrieval

Data pertaining to the stimulation protocol, stimulation medications, and an evaluation of the endometrium for each subject will be recorded retrospectively on the **ART Treatment** eCRF form.

6.3.2 Oocyte Retrieval, Insemination, and Day 1 Fertilization Check

Oocyte retrieval and insemination will follow the standard protocol in place at each trial site. Data will be recorded on the **Oocyte Retrieval and Insemination/Fertilization** eCRF including:

- Date and time of oocyte retrieval
- Number of oocytes retrieved
- Andrology information
- Insemination method
- Total number of normally fertilized eggs (2PN)
- Culture conditions (including gas phase, media, and protein, etc.)
- Embryo morphological grading may be assessed on Day 2 as per local laboratory standard practice in those subjects randomized to the Morphology group only.

6.3.3 Embryo Day 3

Day 3 embryo morphological grading will be performed according to standard protocol and laboratory procedure manual. Eeva results will be printed and used per the Instructions for Use. Data collected will be recorded on the **Day 3 Laboratory Data** eCRF including:

- Date and time of evaluation
- Type of Eeva Petri Dish (number of micro-wells)

- Eeva micro-well identification
- Cell stage and Morphology grading
- Eeva results
- Number of cells after 42 hours, up to the morning of day 3
- Fate of each embryo (Transferred, Cryopreserved, Discarded or extended culture to Day 5/6)
- Eeva Petri Dish and Scope information
- Culture conditions

6.3.4 Embryo Transfer

Embryo transfer will follow the standard protocol in place at each clinical trial site. Data pertaining to the Day 3 or Day 5/6 embryo transfer procedure will be recorded on the **Transfer and Treatment Outcome** eCRF for all patients (Eeva and non-Eeva ones) including:

- Date and day of transfer
- Luteal phase support
- Use of ultrasound
- Final number of embryos transferred

6.3.5 Embryo Day 5-6

If any embryos are cultured to Day 5 or Day 6, data will be recorded on the **Day 5-6 Laboratory Data** eCRF including:

- Date and time of evaluation
- Type of Eeva Petri Dish (number of micro-wells)
- Eeva micro-well identification
- Development stage and Morphology grading
- Fate of the embryo (Transferred, Cryopreserved, Discarded or extended culture to Day 5/6)
- Eeva Petri Dish and Scope information
- Culture conditions

6.3.6 Post Oocyte Retrieval or Post Transfer Day 12-18

The institution's standard urine or blood serum pregnancy testing results (biochemical pregnancy assessed between days 12 and 18) will be recorded on the **Transfer and Treatment Outcome** eCRF including:

- Date of the biochemical pregnancy test
- Pregnancy test results
- Quantitative β hCG, as applicable

If the result of the pregnancy test is negative, the subject will have completed the trial and be exited at that time (complete **Trial Exit** electronic case report form).

6.3.7 Gestational Age Week 5-8

The first ultrasound to verify clinical pregnancy will be recorded on the **Transfer and Treatment Outcome** eCRF including:

- Date of ultrasound
- Result of initial pregnancy ultrasound
 - Number of intrauterine gestational sacs
 - Number of fetal heartbeats

If the result of the ultrasound is negative, that is, if no fetal heartbeat is detected, then the subject will have completed the trial and be exited at that time (complete **Trial Exit** electronic case report form).

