4.1 Primary

The primary objective of the trial is to compare the rate of implantation for Day 3/5 embryo transfers using Eeva scores plus morphology grading versus Day 3/5 embryo transfers using morphology grading only. Implantation rates are calculated by dividing the number of gestational sacs with fetal heart beat identified by ultrasonography at weeks 5 to 8 by the number of embryos transferred on Days 3 or 5.

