7.6.2 Analysis of Primary Endpoint(s)

The crude estimate of the implantation for each embryo assessment method will be calculated as the ratio of the total fetal sacs identified by ultrasonography at weeks 5 to 8 and number of embryos transferred. The approximate 95 % confidence interval of implantation for each embryo assessment method will be calculated. The difference between the methods will be analyzed in an exploratory way using a Poisson regression model. Details regarding the model and analysis approach will be specified in the SAP.

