5.4.8 Gestational Age Week 5-8 (Transfer and Treatment Outcome eCRF)

Result of initial pregnancy ultrasound; Number of intrauterine gestational sacs; Number of fetal heartbeats. If the result of the ultrasound is negative (no fetal heartbeat is detected), the subject stops

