14.1 Primary analysis

Implantation rate will be analyzed with two definitions

First definition: The IR (at embryo level) corresponding to a group of patients is calculated as the ratio of the total fetal sacs (nFS) identified by ultrasonography at weeks 5 to 8 divided by the number of embryos transferred (nET), thus $IR = nFS/nET$.

Alternative Definition of Implantation Rate: The previous (and usual) calculation of IR as mentioned in the protocol ($IR = nFS/nET$) has problems, in particular the implanted embryos are not independent. The international definition used by WHO in particular (see for instance <http://www.advancedfertility.com/ivf.htm>) is: The alternative definition IR^* at women level is $IR_w = nFS_w/nET_w$ and $IR^* = (1/n) \cdot \sum_{w=1,n} IR_w$.

Note: The two definitions IR and IR^* coincide in some cases, in particular for elective Single Embryo transfer eSET (where only one embryo is transferred) or when KID sample is used, but in the general case (ITT sample for instance, IR and IR^* will be different).

The point estimate and 95% CI of IR and IR^* will be calculated in both groups EMG and MG for the ITT selection. No inferential comparison will be conducted between these two groups (as this study is purely descriptive).

The following sections are considered as secondary analyses.

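### A woman whose first week 5-8 scan shows a sac but no heartbeat is closed out, with no place to record a repeat scan before the end of week 8

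*Protocol*

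**What the plan says.** **The exit rule.** Protocol 6.3.7 concerns one scan: "The first ultrasound to verify clinical pregnancy will be recorded on the" Transfer and Treatment Outcome eCRF. It may fall anywhere in gestational weeks 5 to 8. The rule is: "If the result of the ultrasound is negative, that is, if no fetal heartbeat is detected, then the subject will have completed the trial". SAP 5.4.8 repeats it: "If the result of the ultrasound is negative (no fetal heartbeat is detected), the subject stops". Sacs and heartbeats are recorded as separate counts (Protocol 6.3.7; SAP section 17, Nsac and Nhbt), so the data can show a sac without a heartbeat.

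**Later scans.** Protocol 6.3.9 says: "Any additional vaginal ultrasounds performed after 8 weeks may be recorded on an" Additional Ultrasound eCRF, and makes this optional. Protocol 6.3.8 seeks pregnancy outcome only for women who were pregnant at their latest scan. Protocol 5.1, however, allows for results of ultrasounds after the 5-8 week visit. The opening of Protocol section 6 has outcomes collected for all subjects until pregnancy is verified, up to 8 weeks after transfer.

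**Implantation.** Two definitions stand side by side.
- Heartbeat required: Protocol 4.1 ("number of gestational sacs with fetal heart beat identified by ultrasonography at weeks 5 to 8") and 6.1 ("Implantation rate (number of sacs with fetal heart beat/ total number of embryos transferred").
- Sac sufficient: Protocol 7.4.1 and 7.6.2 ("ratio of the total fetal sacs identified by ultrasonography at weeks 5 to 8 and number of embryos transferred") and SAP 14.1 ("ratio of the total fetal sacs (nFS) identified by ultrasonography at weeks 5 to 8 divided by the number of embryos transferred (nET").

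**Other endpoints.** Clinical pregnancy is given a time but no sac or heartbeat criterion. Ongoing pregnancy is assessed at weeks 10 to 12 (Protocol 4.2, 7.4.2; SAP 5.2). Protocol 7.6.1 rules out imputation.

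**The concern.** The rule takes one reading, at a time the site chooses within a four-week window, and treats the absence of a heartbeat as final. If a viable pregnancy can show a sac before it shows a heartbeat, a woman scanned early is closed as negative, and a repeat scan by the clinic a week or two later has no form to go on.

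Three results would be affected:
- The heartbeat-based implantation rate would partly reflect when sites scan.
- Clinical pregnancy could be coded negative, because the only working criterion is the positive or negative scan result (US1 in SAP section 17). Multiple pregnancy, which Protocol 6.1 builds on clinical pregnancy, would follow.
- The woman would leave before weeks 10 to 12, so neither an ongoing pregnancy nor a later miscarriage would be captured.

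The SAP's product is a point estimate and 95% interval in each arm, so an error in the absolute rates matters even when both arms share it.

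**Working it through.** **1. One woman through the rules.** Take a first scan in the window with one sac and no heartbeat.

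| Place | Result for her |
|---|---|
| Protocol 6.3.7, SAP 5.4.8 | Negative; exits |
| Protocol 4.1, 6.1 | 0 implantations |
| Protocol 7.4.1, 7.6.2, SAP 14.1 | 1 implantation |
| Clinical pregnancy (US1) | Criterion not stated; negative if 6.3.7 governs |
| Protocol 6.3.9 | No entry for a repeat scan before the end of week 8 |
| Ongoing pregnancy, weeks 10-12 | No required assessment after exit |
| Protocol 5.1, opening of section 6 | Suggest that later results should count |

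The same woman can be a success in the SAP's primary analysis and a negative exit under the SAP's own visit rule.

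**2. The plan's precision figures.** Protocol 7.2 gives the distance from the rate to its 95% limit. The formula is 1.96 × √(p(1−p)/n), with one embryo per subject. At p = 0.35:
- n = 500: 1.96 × √(0.35 × 0.65/500) = 4.18 points (stated 4.2).
- n = 1000: 1.96 × √(0.35 × 0.65/1000) = 2.96 points (stated 3.0).

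All ten entries in that table reproduce to one decimal.

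**3. Size under the heartbeat definition.** Let f be the share of viable implantations with no heartbeat visible at the first scan. The documents give no value for f, nor the distribution of scan dates, so f is an assumption. Observed rate = p(1−f); downward bias = p × f. At p = 35%:

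| f | Observed | Bias, points |
|---|---|---|
| 1% | 34.65% | 0.35 |
| 2% | 34.30% | 0.70 |
| 5% | 33.25% | 1.75 |
| 10% | 31.50% | 3.50 |

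The bias equals the half-width when f = half-width/p. At 35% that is 2.956/35 = 8.4% for 1000 subjects and 4.18/35 = 11.9% for 500. Over true rates of 45% down to 25%, the ranges are 6.9% to 10.7% and 9.7% to 15.2%.

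In numbers of women, with one embryo each and 1500 women, f = 5% at 35% is 1500 × 0.35 × 0.05 = 26 viable pregnancies exited (19 at a rate of 25%, 34 at 45%).

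**4. Size under the sac definition.** A sac already visible is counted whether or not a heartbeat is seen. The bias is zero for any f.

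**5. Between arms.** With equal f, a true difference of 40% against 35% shrinks from 5 points to 5 × 0.95 = 4.75 (f = 5%) or 5 × 0.90 = 4.5 (f = 10%). With no true difference at 35%, but f = 10% in one arm and 5% in the other, the observed rates are 31.5% and 33.25%, a spurious 1.75 points.

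**The case against.** **The SAP counts sacs, so nothing is scored as a failure.** This stands for the SAP's implantation analysis. A reader of 6.3.7 might infer that the trial's primary estimate is biased downward. For visible sacs, SAP 14.1 does not support that. The objection does not reach the heartbeat-based definition in Protocol 4.1 and 6.1, clinical pregnancy, or follow-up after exit.

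**The premise is not in the documents.** Also correct. Neither document says when a heartbeat can be expected or how first scans fall over weeks 5 to 8. That normal pregnancies are being lost is a risk under an assumption, not something the plan demonstrates.

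**Later scans were meant to count.** Protocol 5.1, the opening of section 6, and the SAP's final-outcome variable (Outc, with separate miscarriage and ongoing codes) point that way. They conflict with the immediate exit in 6.3.7 and provide no form for a scan between the first one and week 8. They support reconciliation and do not close the gap.

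**Week 10-12 data are weak for every pregnant woman.** Scans after week 8 are optional, Protocol 5.1 leaves follow-up endpoints out of the completion timeline, 6.4.1.2 plans no pregnancy follow-up, and section 12 closes the trial on the 5-8 week data. The exit rule adds to an existing weakness by an amount that cannot be calculated.

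**Bias between arms is speculative.** Yes. Protocol 7.13 says the trial is unblinded, and a reader might infer that scan timing differs by arm. No passage links timing to allocation.

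**Conclusion.** The concern holds for the rule and the gap, and is of moderate importance. As written, a woman with a sac but no heartbeat at her first scan is closed out. She counts as no implantation under Protocol 4.1 and 6.1, may be coded negative for clinical pregnancy, and has no required assessment for ongoing pregnancy or miscarriage. She remains an implantation in the SAP's sac-based analysis.

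The numerical size rests on the assumed f and on the heartbeat definition. For f from 1% to 10% at a true 35%, the loss is 0.35 to 3.5 points. It is well inside the stated half-widths at the low end and above the 3.0 points of the Eeva arm at the high end. A difference between arms arises only if scan timing or rescanning differs by arm. The text and the missing data route are certain; how many women are affected is not known.

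**What to change.** 1. Reconcile Protocol 6.3.7 and SAP 5.4.8 with Protocol 5.1, the opening of section 6 and 6.3.8, so that the trial record of a woman with a sac but no heartbeat at the first scan stays open for data capture.
2. On the existing Transfer and Treatment Outcome eCRF, record any scan the clinic already performs up to the end of week 8, with date and gestational age. Let those results determine heartbeat status, clinical pregnancy, and eligibility for ongoing-pregnancy and miscarriage follow-up.
3. Reconcile Protocol 4.1 and 6.1 with 7.4.1, 7.6.2 and SAP 14.1 on whether implantation requires a heartbeat.
4. Do not by default replace an earlier scan's sac count with that of the last scan. Doing so would drop sacs seen earlier and make the rate depend on how often a site rescans.
5. State in the SAP how a woman is classified when her only scan shows a sac without a heartbeat, since recording existing scans will not resolve her status.

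The cost is a short wording change in both documents, repeatable scan fields on one eCRF page, and a few records open for longer. No scan is added and clinical management is unchanged.
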